## Myeloproliferative Neoplasm Symptom Assessment Form (MPN-SAF)

**Instructions:** Please circle the number corresponding with how each symptom as affected you.

### Symptom

**1 to 10 (0 if absent) ranking\***  
**1 is most favorable and 10 least favorable**

Please rate your fatigue  
(weariness, tiredness) by circling  
the one number that best  
describes your fatigue right  
NOW

(No Fatigue) 0 1 2 3 4 5 6 7 8 9 10 (Worst Imaginable)

Please rate your fatigue  
(weariness, tiredness) by circling  
the one number that best  
describes your USUAL level of  
fatigue during past 24 hours

(No Fatigue) 0 1 2 3 4 5 6 7 8 9 10 (Worst Imaginable)

Please rate your fatigue  
(weariness, tiredness) by circling  
the one number that best  
describes your WORST level of  
fatigue during past 24 hours

(No Fatigue) 0 1 2 3 4 5 6 7 8 9 10 (Worst Imaginable)

**Circle the one number that describes how, during the past 24 hours,  
fatigue has interfered with your**

- General activity (Does not Interfere) 0 1 2 3 4 5 6 7 8 9 10 (Completely Interferes)
- Mood (Does not Interfere) 0 1 2 3 4 5 6 7 8 9 10 (Completely Interferes)
- Walking ability (Does not Interfere) 0 1 2 3 4 5 6 7 8 9 10 (Completely Interferes)
- Normal work (includes
- work both outside the (Does not Interfere) 0 1 2 3 4 5 6 7 8 9 10 (Completely Interferes)
- home and daily chores)
- Relations with other
- people (Does not Interfere) 0 1 2 3 4 5 6 7 8 9 10 (Completely Interferes)
- Enjoyment of life (Does not Interfere) 0 1 2 3 4 5 6 7 8 9 10 (Completely Interferes)

**Circle the one number that describes how, during the past Week how  
much difficulty you have had with each of the following symptoms**

---

Filling up quickly when you eat (Early satiety)	(Absent) 0 1 2 3 4 5 6 7 8 9 10 (Worst Imaginable)
Abdominal pain	(Absent) 0 1 2 3 4 5 6 7 8 9 10 (Worst Imaginable)
Abdominal discomfort	(Absent) 0 1 2 3 4 5 6 7 8 9 10 (Worst Imaginable)
Inactivity	(Absent) 0 1 2 3 4 5 6 7 8 9 10 (Worst Imaginable)
Problems with headaches	(Absent) 0 1 2 3 4 5 6 7 8 9 10 (Worst Imaginable)
Problems with concentration - Compared to prior to my MPD	(Absent) 0 1 2 3 4 5 6 7 8 9 10 (Worst Imaginable)
Dizziness/ Vertigo/ Lightheadedness	(Absent) 0 1 2 3 4 5 6 7 8 9 10 (Worst Imaginable)
Numbness/ Tingling (in my hands and feet)	(Absent) 0 1 2 3 4 5 6 7 8 9 10 (Worst Imaginable)
Difficulty sleeping	(Absent) 0 1 2 3 4 5 6 7 8 9 10 (Worst Imaginable)
Depression or sad mood	(Absent) 0 1 2 3 4 5 6 7 8 9 10 (Worst Imaginable)
Problems with sexual desire or Function	(Absent) 0 1 2 3 4 5 6 7 8 9 10 (Worst Imaginable)
Cough	(Absent) 0 1 2 3 4 5 6 7 8 9 10 (Worst Imaginable)
Night sweats	(Absent) 0 1 2 3 4 5 6 7 8 9 10 (Worst Imaginable)
Itching (pruritus)	(Absent) 0 1 2 3 4 5 6 7 8 9 10 (Worst Imaginable)
Bone pain (diffuse not joint pain or arthritis)	(Absent) 0 1 2 3 4 5 6 7 8 9 10 (Worst Imaginable)
Fever (>100 F)	(Absent) 0 1 2 3 4 5 6 7 8 9 10 (Worst Imaginable)
Unintentional weight loss last 6 months	(Absent) 0 1 2 3 4 5 6 7 8 9 10 (Worst Imaginable)
What is your overall quality of life?	(As good as it can be) 0 1 2 3 4 5 6 7 8 9 10 (As bad as it can be)

**APPENDIX H: EORTC QLQ-C30**

**EORTC QLQ-C30 (version 3)**

We are interested in some things about you and your health. Please answer all of the questions yourself by circling the number that best applies to you. There are no "right" or "wrong" answers. The information that you provide will remain strictly confidential.

Please fill in your initials:    
 Your birthdate (Day, Month, Year):     
 Today's date (Day, Month, Year): 31

	Not at All	A Little	Quite a Bit	Very Much
1. Do you have any trouble doing strenuous activities, like carrying a heavy shopping bag or a suitcase?	1	2	3	4
2. Do you have any trouble taking a long walk?	1	2	3	4
3. Do you have any trouble taking a short walk outside of the house?	1	2	3	4
4. Do you need to stay in bed or a chair during the day?	1	2	3	4
5. Do you need help with eating, dressing, washing yourself or using the toilet?	1	2	3	4

**During the past week:**

	Not at All	A Little	Quite a Bit	Very Much
6. Were you limited in doing either your work or other daily activities?	1	2	3	4
7. Were you limited in pursuing your hobbies or other leisure time activities?	1	2	3	4
8. Were you short of breath?	1	2	3	4
9. Have you had pain?	1	2	3	4
10. Did you need to rest?	1	2	3	4
11. Have you had trouble sleeping?	1	2	3	4
12. Have you felt weak?	1	2	3	4
13. Have you lacked appetite?	1	2	3	4
14. Have you felt nauseated?	1	2	3	4
15. Have you vomited?	1	2	3	4
16. Have you been constipated?	1	2	3	4

Please go on to the next page

**During the past week:**

	Not at All	A Little	Quite a Bit	Very Much
17. Have you had diarrhea?	1	2	3	4
18. Were you tired?	1	2	3	4
19. Did pain interfere with your daily activities?	1	2	3	4
20. Have you had difficulty in concentrating on things, like reading a newspaper or watching television?	1	2	3	4
21. Did you feel tense?	1	2	3	4
22. Did you worry?	1	2	3	4
23. Did you feel irritable?	1	2	3	4
24. Did you feel depressed?	1	2	3	4
25. Have you had difficulty remembering things?	1	2	3	4
26. Has your physical condition or medical treatment interfered with your family life?	1	2	3	4
27. Has your physical condition or medical treatment interfered with your social activities?	1	2	3	4
28. Has your physical condition or medical treatment caused you financial difficulties?	1	2	3	4

**For the following questions please circle the number between 1 and 7 that best applies to you**29. How would you rate your overall health during the past week?

1      2      3      4      5      6      7

Very poor

Excellent

30. How would you rate your overall quality of life during the past week?

1      2      3      4      5      6      7

Very poor

Excellent

**APPENDIX I: National Cancer Institute Common Terminology Criteria for Adverse Events (NCI CTCAE)**

The United States of America (USA) National Cancer Institute Common Terminology Criteria for Adverse Events, version 4.0 (NCI CTCAE, v.4.0) can be found on the following website.

[http://ctep.cancer.gov/protocolDevelopment/electronic\\_applications/ctc.htm#ctc\\_40](http://ctep.cancer.gov/protocolDevelopment/electronic_applications/ctc.htm#ctc_40)

[Accessed: 13 February 2013]

This version of CTCAE is compatible at the AE (Adverse Event) term level where each CTCAE term is a Medical Dictionary for Regulatory Activities Terminology (MedDRA) LLT (Lowest Level Term). CTCAE v4.0 includes 764 AE terms and 26 'Other, specify' options for reporting text terms not listed in CTCAE. Each AE term is associated with a 5-point severity scale. MedDRA v12.0.

**APPENDIX J: STAGE 2 EXTENSION STUDY**

Sponsor: Promedior, Inc.
Name of Finished Product: Recombinant human Pentraxin-2; PRM-151
Study Title: A Phase 2, - Prospective Study of PRM-151 In Subjects With Primary Myelofibrosis (PMF), Post-Polycythemia Vera MF (post-PV MF), or Post-Essential Thrombocythemia MF (post-ET MF)
Study Number: PRM-151G-101
Study Phase: Phase 2
Investigational Product; Dose; and Mode of Administration: PRM-151 10 mg/kg intravenous
Comparator; Dose; and Mode of Administration: Not applicable
Primary Objective(s): To provide subjects in the parent study an opportunity to remain on treatment and to allow all subjects to switch to an open label extension utilizing the 10 mg/kg dose after completing 9 cycles of the originally assigned treatment.
Secondary Objective(s): 
 
• To collect long term safety data of subjects receiving PRM-151
 
• To collect additional efficacy data on duration of response beyond 36 weeks of treatment
 
• To collect efficacy data on the change of PRM-151 dose level in subjects not achieving a response
 

Study Design:  This is an open-label extension of study PRM-151G-101 to provide continued access to subjects in the parent study. All subjects completing 9 cycles of the originally assigned

treatment may switch to an open label extension and receive PRM-151 10mg/kg every 4 weeks. The first cycle of the open label phase contains a loading dose of 10mg/kg on days 1,3 and 5. This will allow for subjects from all three dosing cohorts to receive a loading dose of 10mg/kg while maintaining the blind. Additionally, subjects who have entered the open label extension study prior to the approval of this amendment may receive a loading dose (10 mg/kg on days 1, 3, and 5), to be administered on their next scheduled cycle after approval of this protocol amendment. This will allow for these subjects to receive any potential pharmacologic benefit of the loading dose.

**Study Duration:**

Subjects may continue with PRM-151 dosing in the absence of disease progression or toxicity warranting discontinuation of therapy until drug is made available in another way. Cycle numbers will continue from the parent protocol, with cycle 9 Day 29 of the parent protocol becoming Cycle 10 Day 1 of the extension study.

**Response Assessments:**

In addition to the schedule of assessments listed below, response assessments will be done on Day 1 of every third cycle (every 12 weeks) beginning on Day 1 of Cycle 13 and may include the following, as described below:

**Bone Marrow Biopsies:**

An optional bone marrow biopsy will be performed every 12 weeks.

**MPN SAF and EORTC QLQ-C30:**

Symptoms will be assessed using the MPN SAF and EORTC QLQ-C30 on Day 1 on every cycle.

**Physical Exam and Spleen Measurement:**

An abbreviated physical exam and spleen measurement by palpation will be done on Day 1 of every cycle.

**PET-CT or CT or MRI:**

These will be performed every 24 weeks.

Stage 2 Extension Study SCHEDULE OF ASSESSMENTS	Cycle 10  (Cycle 9, Day 29)	Extension Cycles 28 Day Cycle Length
	Day 1 (+/-3 days)	Day (+/- 3 days)
	1	3
	5	1

Informed Consent	x			
AE/SAE assessment (1)	x	x	x	x
Physical Exam (2)	x			x
Prior/Con Meds	x	x	x	x
Special list of excluded medications	x	x	x	x
Vital Signs (3)	x	x	x	x
Weight (kg)	x			x
ECOG Performance Score	x			x
Urine Pregnancy Test	x			x
Complete Blood Count (4)	x			x
Chemistry, BUN/creatinine (5)	x			x
Coagulation (6)	x			x
Review transfusion diaries	x			x
Bone Marrow (7)	x			x
MPN-SAF score (7)	x			x
EORTC-QLQC30 (7)	x			x
PET-CT Scan of CT or MRI (8)	x			x
Anti-pentraxin 2 antibodies, pre-dose (9)	x			x
Pentraxin-2 levels, pre-dose (9)	x			x
Access IRS (10)	x	x	x	x

PRM-151 Administration 	X	X	X	X
--	---	---	---	---

1. Pre-treatment adverse events, including serious adverse events will be collected from the time of informed consent and after the medical history has been obtained.
2. Abbreviated physical exam and spleen measurement by palpation will be done day 1 of every cycle.
3. Vital signs (including temperature, blood pressure, pulse rate, and respiratory rate) will be performed before and immediately after PRM-151 infusion, and at the conclusion of the one hour observation period.
4. CBC includes red blood cell count (RBC), hemoglobin, hematocrit, white blood cell count with differential, absolute neutrophil count (ANC), reticulocyte count, last count, and platelets.
5. Blood chemistry lab parameters include lactic dehydrogenase (LDH), serum alanine aminotransferase (ALT), serum aspartate aminotransferase (AST), direct and indirect bilirubin, alkaline phosphatase, creatinine phosphokinase (CPK), uric acid, calcium, phosphorus, sodium, potassium, chloride, albumin, bicarbonate, BUN, creatinine, and glucose.
6. Coagulation testing at screening for all subjects to include prothrombin time (PT), and partial thromboplastin time (PTT). For subjects receiving warfarin, the PT, PTT and international normalized ratio (INR) must be obtained. Abnormal INRs will be tested twice weekly until the INR is stable for one month, followed by monthly monitoring of INRs
7. MPN-SAF EORTC QLQ-C30, will be performed on Day 1 of every cycle. Bone marrow biopsy window +/- 6 weeks.
8. PET-CT Scan or CT or MRI will be performed every 24 weeks.
9. Blood sample for pentraxin-2 and anti-pentraxin 2 antibodies should be drawn pre-dose every 12 weeks. If the subject experiences an infusion related reaction, a blood sample for anti-pentraxin 2 antibodies should be drawn prior to any subsequent PRM-151 infusions. A blood sample for cytokines and anti-pentraxin 2 antibodies may be obtained in the event of a suspected adverse reaction as well.
10. For consistency, the unblinded pharmacist will continue to access IRS to confirm occurrence of dosing on Day 1 of each Cycle.
11. Subjects will be observed one hour after each dose.
12. Loading dose of 10 mg/kg on Days 1, 3 and 5. Alternative loading dose schedule is Days 1, 3 and 6 when days 1, 3 and 5 are not possible. Additionally, subjects who have entered the open label extension study prior to the approval of this amendment may receive a loading dose (10 mg/kg on days 1, 3, and 5), to be administered on their next scheduled cycle after approval of this protocol amendment.

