#### **8.5 Cycle 9, Day 29 (Week 36) (+/- 3 days)**

- MPN-SAF
- EORTC QLQ-C30
- IWG-MRT DIPSS (risk assessment)
- IWG-MRT Response Assessment (PMF, post-EV MF and post PV MF patients)
- PET-CT or CT or MRI (+/- 3 days)
- Bone marrow biopsy (+/- 3 days)
- Abbreviated physical exam with spleen measurements
- Recording of concomitant medications
- Monitoring of adverse events
- Vital signs
- ECOG Performance Status
- Complete blood count (CBC) (central lab)

- Chemistry evaluations (central lab)
- Coagulation parameters (central lab)
- Review of transfusions
- Review of excluded medications
- Blood sample for pentraxin-2 levels (pre-dose if continuing treatment in extension)
- Blood sample for anti-pentraxin 2 antibody (pre-dose)
- Blood samples for genetic analysis

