**APPENDIX A Schedule of Events**

	Screening < 28 days	Cycle 1 28 Day Cycle Length			Cycle 2, 3, 4, 5, 6, 7, 8, 9, 28 Day Cycle Length	Cycle 9, Day 29	End of Study 
		Day (+/- 1 day)			Day (+/- 3 days)	(+/- 3 days)	(+/- 3 days)
		1	3	5	1		
Informed Consent	x						
Demographics	x						
Past Medical History	x	x					
Inclusion/Exclusion	x	x					
Bone Marrow Biopsy 	x				x	x	
Physical Exam 	x	x			x	x	x
IWG-MRT Response Assessment					x	x	
Prior/Concomitant Medications	x	x	x	x	x	x	x
Transfusion history (previous 12 weeks and between screening visit)	x	x			x	x	x
Review of transfusion diaries	x	x			x	x	x
AE/SAE Assessment 	x	x	x	x	x	x	x
Vital Signs 	x	x	x	x	x	x	x
Height (cm)	x						
Weight (kg)	x	x			x		
ECOG Performance Score	x	x	x	x	x	x	x
Pregnancy test 	x	x			x		
Complete Blood Count 	x	x			x	x	x
Chemistry, BUN/creatinine 	x	x			x	x	x
Coagulation 	x	x			x	x	
12 lead ECG 	x						
PET-CT Scan or CT or MRI 		x			x	x	
Exploratory laboratory assessments 		x				x	
Special list of excluded medications	x	x			x	x	x
Anti-pentraxin 2 antibodies, pre-dose		x			x	x	
Pentraxin-2 , pre-dose		x			x	x	
MPN-SAF 	x	x			x	x	x
EORTC-QLQC30 	x	x			x	x	x
Access IRS 	x	x	x	x	x		
IWG-MRT DIPPS (risk assessment)	x	x				x	

PRM-151 Administration 		X	X	X	X		
Infusion Related Reaction Cytokines and anti-pentraxin 2 antibodies 		X					

- 1 Bone marrow biopsy at Screening must have been performed within 4 weeks prior to first infusion of PRM-151; subsequent bone marrow biopsies on Cycle 4, Day 1, Cycle 7, Day 1 and on Cycle 9, Day 29 performed +/- 3 days of scheduled visit
- 2 Abbreviated physical exam including spleen measurement by palpation at all time points
- 3 Pre-treatment adverse events, including serious adverse events will be collected from the time of informed consent and after the medical history has been obtained
- 4 Vital signs (including temperature, blood pressure, pulse rate, and respiratory rate) will be performed before and immediately after PRM-151 infusion ,and at the conclusion of the one hour observation period
- 5 Serum pregnancy test within 4 weeks prior to the first dose of the study drug (central lab) Urine pregnancy test at all subsequent time points (local lab)

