4.8 OLE STUDY ANALYSES

The OLE analyses will be performed separately for the OLE Stage 1 and Stage 2.

The listings will include the treatment regimen the patient received during the main stage and during the OLE.

For Stage 1, OLE begins with the first infusion of Cycle 7. As with the main study, cycles are 28 days in length. The "OLE Baseline" consists of assessments at the end of Cycle 6 / beginning of Cycle 7 (pre-dose).

For Stage 2, OLE begins with the first infusion of Cycle 10. As with the main study, cycles are 28 days in length. The "OLE Baseline" consists of assessments at the end of Cycle 9 / beginning of Cycle 10 (pre-dose).

The synopses for the OLE are in Appendix 2 and Appendix 4.

The primary and secondary endpoints for both stages, will be also produced on the OLE population when applicable. The OLE tables will be classified as per the original dose

received on the main stage and overall. For subjects who change doses, improvement will be analyzed.

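### The Week 36 bone marrow biopsy carries two conflicting windows (+/-3 days and +/-6 weeks) and no pre-dose condition, so it could be taken after 10 mg/kg extension dosing has begun

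*Protocol*

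**What the plan says.** Main stage. Protocol Appendix A, footnote 1, has the last biopsy on "Cycle 9, Day 29 performed +/- 3 days of scheduled visit". Section 8.5 repeats the +/-3 days, and SAP Appendix 6 reproduces Appendix A.

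Extension. Appendix J, Study Duration, continues the cycle numbering, "with cycle 9 Day 29 of the parent protocol becoming Cycle 10 Day 1 of the extension study". The first column of the Appendix J schedule is labelled with both names and headed Day 1 (+/-3 days). The bone marrow row is marked in that column under footnote 7, which says "Bone marrow biopsy window +/- 6 weeks". SAP Appendix 4 carries the same table and footnote.

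Dosing after the visit. Subjects completing nine cycles "may switch to an open label extension and receive PRM-151 10mg/kg every 4 weeks". Footnote 12 adds "Loading dose of 10 mg/kg on Days 1, 3 and 5" for the first extension cycle.

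Order within the visit. Section 8.5 and Appendix J mark the pentraxin-2 and antibody samples as pre-dose. Neither marks the biopsy that way.

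Analysis. SAP 4.8 starts the Stage 2 OLE at the first infusion of Cycle 10 and takes the OLE baseline from "assessments at the end of Cycle 9 / beginning of Cycle 10 (pre-dose". SAP 4.4.1 defines bone marrow response as a one-grade reduction from baseline at any time of the study. It gives no biopsy window and does not refer to the 4.8 boundary.

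**The concern.** One biopsy at one visit has two permitted ranges, 3 days and 42 days either side. Protocol section 7 sends Stage 2 evaluations to Appendix A and extension subjects to Appendix J, and this visit belongs to both. A site working from Appendix J could take the Week 36 biopsy as late as Week 42 and be within its schedule. By then a subject from a lower-dose arm who entered the extension has switched to 10 mg/kg.

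That biopsy serves four purposes: the any-time primary response, the Week 36 response rate, the between-dose comparison (which the synopsis places at Week 36), and the extension baseline. Stage 2 has no control arm, and section 1.5 looks to a dose response for evidence of efficacy. A response first seen after the switch but credited to 0.3 mg/kg would narrow that contrast. A post-dose reading is also not the pre-dose baseline that SAP 4.8 describes.

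**Working it through.** **1. The windows for the same visit**

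| Place | Window |
|---|---|
| Protocol 8.5 | +/-3 days |
| Protocol Appendix A, footnote 1 (and SAP Appendix 6) | +/-3 days |
| Appendix J, column header | Day 1 +/-3 days |
| Appendix J, footnote 7 on the bone marrow row (and SAP Appendix 4) | +/-6 weeks |

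None of these states that the biopsy comes before the infusion.

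**2. Extension doses that can precede the biopsy**

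Count Cycle 10 Day 1 as day 1. The 10 mg/kg doses fall on days 1, 3, 5, 29, 57 and so on; Appendix J also allows days 1, 3, 6. The latest biopsy day is 1 + window.

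- +6 weeks: day 1 + 42 = 43. Doses already given: days 1, 3, 5 (or 6) and 29, so four. The next dose is due on day 57, or day 54 at the earliest with its own visit window, and falls outside.
- +3 days: day 1 + 3 = 4. Doses already given: days 1 and 3, so two.
- Biopsy before the first infusion: none.

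A subject who entered the extension before the amendment and loads in the next cycle (days 1, 29, 31, 33) also reaches four by day 43. The shorter window alone therefore does not guarantee a reading on the assigned dose; only a pre-dose condition does.

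**3. The plan's own power figure**

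Inputs from protocol 10.1: 24 per arm, two-sided alpha 0.025 (z = 2.241), best rate 46%, difference 39 points, so 46% vs 7%. With p̄ the mean of the two rates and d their difference:

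power = Φ{ [d√n − z√(2p̄(1−p̄))] / √(p₁(1−p₁) + p₂(1−p₂)) }

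For 46% vs 7%: d√n = 0.39 × 4.899 = 1.911; z-term = 2.241 × 0.624 = 1.399; denominator = 0.560. Power = Φ(0.914) = 0.820, which reproduces the stated 82%. For the assumed rates themselves, 46% vs 5%, the same formula gives 0.875.

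**4. Illustration of a shifted low-dose rate**

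Let f be the share of 0.3 mg/kg subjects whose Week 36 biopsy is late, and q the added response probability among those who would otherwise be non-responders. Neither is in the documents; both are assumptions. The low-dose rate becomes 0.05 + 0.95·f·q, and the 10 mg/kg rate is held at 46%.

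| f | q | Low-dose rate | Power, same formula | Power, Fisher exact |
|---|---|---|---|---|
| 0 | – | 5.0% | 87.5% | 85.3% |
| 0.10 | 0.10 | 6.0% | 85.0% | 81.8% |
| 0.25 | 0.20 | 9.8% | 73.0% | 66.2% |
| 0.50 | 0.20 | 14.5% | 55.7% | 46.6% |

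These are unstratified calculations. The planned tests (CMH in the protocol, stratum-adjusted logistic regression in the SAP) would give somewhat different values.

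**The case against.** The strongest reply is that footnote 7 was never meant for this visit. Appendix J describes an optional biopsy every 12 weeks and starts extension response assessments at Cycle 13. Six weeks is half of 12, a natural tolerance for that schedule, and the disputed column is itself headed +/-3 days. This is probably what was intended. It does not settle the text, because the Cycle 10 Day 1 bone marrow cell carries the footnote and nothing there restricts it.

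A second reply is that SAP 4.8 already draws the line. The OLE begins with the first Cycle 10 infusion, and SAP section 2 says that Stage 2 means the main stage unless the OLE is named. Read together, these would place a later biopsy in the OLE. This has real weight. What it leaves open is that 4.4.1 does not apply the boundary to its any-time definition, and no rule covers a biopsy labelled Week 36 but taken after that infusion. An earlier Stage 2 SAP (Version 2.0, March 2018) may define visit windows; it is not among these documents.

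Third, the conditions are narrow. The subject must enter an optional extension and be biopsied late. For the any-time endpoint the subject must also have been a non-responder at Weeks 12 and 24. The 0.3 mg/kg arm is not part of the protocol's primary test against 10%, and its comparison with the higher doses is secondary there, although SAP 4.4.1 lists it under the primary endpoint. All of this stands and limits the size of the problem. The 3 mg/kg arm is in the test against 10%, however, and its subjects switch too.

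**Conclusion.** The contradiction is real and should be reconciled. It is a should-fix clarification, not a defect that undermines the trial. As written, Appendix J lets the Week 36 biopsy follow up to four 10 mg/kg doses in a 0.3 or 3 mg/kg subject who enters the extension, and even +/-3 days allows two.

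A reader might infer that low-dose subjects' main-stage endpoint is in fact read on another dose. The documents do not support that. They show what is permitted on one reading of a footnote, not that late biopsies occurred. Nor do they show that up to six weeks at 10 mg/kg changes fibrosis grade: the first on-treatment biopsy is at Week 12, and subjects count as evaluable only after twelve weeks on drug. The large gap in cumulative dose (up to 4 × 10 = 40 mg/kg after the switch, against 11 × 0.3 = 3.3 mg/kg in the low-dose main stage) measures exposure, not effect.

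A reader might also take the power losses as a forecast. They are not: the fall to about 85% or about 56% depends wholly on assumed shares of late biopsies and added response. The effect on the 0.3 mg/kg contrast would be towards no difference. The Week 36 rate and the OLE baseline are more exposed than the any-time response, because an earlier response does not protect them.

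**What to change.** In Protocol Appendix J, footnote 7, and its copy in SAP Appendix 4, limit the +/-6 week window to the later optional extension biopsies. State that the Cycle 9 Day 29 / Cycle 10 Day 1 biopsy keeps +/-3 days and is taken before the first extension infusion; add the same pre-dose condition in section 8.5 and Appendix A.

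In SAP 4.4.1 and 4.8, state that a biopsy taken after the first Cycle 10 infusion is assigned to the OLE and is not used for main-stage Stage 2 response or as the OLE baseline. The SAP change remains useful even if the protocol edit comes late, because this SAP governs the final analysis of both main Stage 2 and its OLE.

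The cost is a footnote, a pre-dose condition and one SAP rule. A few late Week 36 biopsies would leave the main-stage analysis. Their number should be reported by arm, and subjects left with no readable post-baseline biopsy would count as non-responders under the existing SAP rule. No change to dosing is involved.
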